Feelings about Exercise: Protocol

NCT03598647

1/23/19

Background and objectives

Despite the numerous health benefits of regular physical activity (PA), >50% of adults are insufficiently active. Understanding why some individuals choose to engage in PA while others do not is important for informing the development of future PA interventions. Previous research has demonstrated that those who have more positive affective responses to exercise (i.e., the pleasure or displeasure experienced with PA) are more likely to exercise in the future. However, an interesting paradox is that most people generally 'feel good' post-exercise. This begs the questions, if exercise makes people feel good, why don't more people exercise? The answer may lie in one's memory of how exercise makes them feel.

This study seeks to compare exercisers and non-exercisers on their affective responses to exercise, which includes pre-, during, and post-exercise affect, memory of during and post-exercise affect, and anticipated affect towards a future exercise session. It is hypothesized that compared to regular exercisers, non-exercisers will have a more negative memory of how exercise made them feel, and as a result, also have more negative anticipated affect towards a future exercise session. Further, this study seeks to pilot an intervention to improve affective response to exercise among the group of non-exercisers. It is hypothesized that non-exercisers randomized to an affect-based intervention will have a more favorable affective response to exercise following the intervention compared to those randomized to the control intervention (e.g., basic PA recommendations).

Participants

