A total of 59 individuals with overweight/obesity (BMI 25-40 kg/m²), who were weight loss seeking, and between the ages of 18-60 were recruited via self-referral from Internet advertisements. Interested individuals completed a phone screen questionnaire to determine initial eligibility. During this screening, trained research assistants queried potential participants on their moderate-to-vigorous intensity PA (MVPA) over the previous 6 months and a recent 'typical' week. If average MVPA was <30 min/week, the individual was classified as a 'non-exerciser', if average MVPA was ≥150 min/week, the individual was classified as an 'exerciser'. Individuals reporting an intermediate amount of MVPA (30 to <150 min/week) were ineligible for this study as the goal was to target distinctive groups of exercisers vs. non-exercisers. Exclusion criteria included conditions limiting ability to exercise, history of coronary artery disease (i.e., myocardial infarction), stroke, diabetes, pulmonary disease (e.g., COPD), uncontrolled hypertension (i.e., resting BP ≥140/90 mmHg), use of any medication that would affect heart rate (HR; e.g., beta blocker), current enrollment in a weight loss treatment program, history of bariatric surgery, or women who were nursing/pregnant,

Study overview

Individuals deemed eligible based upon the phone screen attended an in-person orientation session in order to learn about the study in greater detail and to provide informed consent in accordance with guidelines set forth by the Internal Review Board of the Miriam Hospital. Upon consenting, participants completed a baseline assessment, which included measures of BMI, fitness, and 1 week of objective physical

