## **Statistical analysis**

Preliminary analyses were conducted to compare the groups (exercisers vs. non-exercisers) with respect to demographic variables including age, BMI, and gender. Chi Square tests were used to assess between-group differences in categorical variables and independent two-sample t-tests were used for continuous variables. First, unadjusted between-group differences in anticipated affect, pre-exercise affect, and post-exercise affect were assessed using independent two-sample t-tests. Next, using a series of longitudinal linear mixed effects models, we examined between-group (exercisers vs. non-exercisers) differences in serial measures of during-exercise affect (5, 10, 15, 20, 25 minutes) and post-exercise affect (immediate and 15 minutes post-exercise). Models included a subject-specific intercept and adjusted for repeated measures within participant over time. A similar analytic strategy was used to examine group differences in recalled affect (1, 3, and 7 days post-exercise). The goal was to determine the degree to which global recalled affect is associated with (i.e., biased toward) affective responses during or after PA and whether this differs between exercisers and non-exercisers. Correlation analysis was used to examine whether affective recall bias was correlated with anticipated affect towards future exercise. Finally, between-subjects ANOVAs were used to compare non-exercisers receiving the brief cognitive intervention to those in the control group on anticipated affect, affective response to exercise session 3, recalled affect for exercise session 2, and minutes/week spent in MVPA (assessed via the armband). All analyses were carried out in SAS 9.3 with significance level set at .05 a priori. Mixed effects models use a likelihood based approach to estimation, thus making use of all available data without directly imputing missing value.

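### The exerciser versus non-exerciser contrast is observational, but the SAP names no demographic covariate in any between-group model, so no planned estimate separates exerciser status from age or gender.

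*SAP*

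**What the plan says.** The Protocol (Participants) forms the groups from a phone-screen report of moderate-to-vigorous activity (MVPA). For the lower group the rule reads "If average MVPA was <30 min/week, the individual was classified as a" non-exerciser. The exerciser group starts at 150 min/week, and people in between are excluded because "the goal was to target distinctive groups of exercisers vs. non-exercisers". Participants are people "who were weight loss seeking, and between the ages of 18-60", and no matching or stratification is stated. Randomisation applies only to the non-exercisers, after Exercise Session 2 (Randomized Controlled Trial for Non-Exercisers).

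The Protocol (Background and objectives) gives the aim of this part as a comparison: "This study seeks to compare exercisers and non-exercisers on their affective responses to exercise, which includes pre-, during, and post-exercise affect". The same section sets a wider purpose: "Understanding why some individuals choose to engage in PA while others do not is important for informing the development of future PA interventions".

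The SAP (Statistical analysis) then takes three steps:

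- Demographics: "Preliminary analyses were conducted to compare the groups (exercisers vs. non-exercisers) with respect to demographic variables including age, BMI, and gender".
- First outcome tests: "First, unadjusted between-group differences in anticipated affect, pre-exercise affect, and post-exercise affect were assessed using independent two-sample t-tests".
- Mixed models for serial during-exercise and post-exercise affect: "Models included a subject-specific intercept and adjusted for repeated measures within participant over time". Recalled affect is handled in a similar way.

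No covariate is named for any of these models, and no action is tied to the preliminary tests. Neither document says that the contrast is descriptive or associational only.

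**The concern.** People who report at least 150 minutes a week and people who report under 30 may differ in age and gender, and both may relate to how people rate their feelings. A subject-specific intercept models the correlation among one person's repeated ratings. It does nothing about a difference in age or gender between the groups. Calling the first tests unadjusted may suggest that adjusted ones follow, but the only adjustment then described is for repeated measures.

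What is at stake is interpretation. If the results are read only as how two types of people differ, the plan suffices. If they are read as bearing on why some people exercise, or on what an intervention should target, age and gender are rival explanations that no planned estimate addresses.

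Memory bias is not exempt. It is recalled minus actual affect within a person (Protocol, Affective Recall and Memory Bias). Differencing removes a stable personal rating tendency, but not an effect of age or gender on recall bias itself.

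**Working it through.** The plan gives no power or effect-size figure for this contrast, so there is none to reproduce.

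**Inputs from the documents.** Total 59; randomised non-exercisers 15 + 15 = 30; exercisers 59 − 30 = 29. The 29 is derived and assumes that every non-exerciser among the 59 was randomised. The significance level is .05; two-sided testing is my assumption.

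**Assumed inputs (not in the documents).** Age imbalance of 0.3, 0.5 or 0.8 SD; a 20-point difference in the proportion of women, from 50% vs 70% up to 70% vs 90%.

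**1. Can the preliminary tests exclude an imbalance?** For age, I use the noncentral t with 57 df and noncentrality d × √(30 × 29 / 59) = 3.84d. For gender, I use the Pearson chi-square by exact binomial enumeration.

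| Assumed imbalance | Power |
|---|---|
| Age 0.3 SD | 21% |
| Age 0.5 SD | 47% |
| Age 0.8 SD | 86% |
| Women 50% vs 70% | 36% |
| Women 60% vs 80% | 41% |
| Women 70% vs 90% | 51% |

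A 0.5 SD age difference is missed 53% of the time. With both imbalances present and the tests treated as independent, the chance of at least one flag is 1 − (1 − age power)(1 − gender power):

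- Age 0.5 SD: 1 − 0.529 × 0.644 = 66%, up to 1 − 0.529 × 0.495 = 74%.
- Age 0.8 SD: 91% to 93%.

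So a moderate imbalance can pass unseen. A large one would usually be seen, but nothing is planned in response.

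**2. What does adjustment cost in precision?** The standard error is multiplied by √(1 + pq·D²). Here pq = (30/59)(29/59) = 0.250, and D² is the squared age difference in SD plus the squared gender difference divided by the within-group gender variance. Age and gender are taken as uncorrelated within group. The gender term is 0.04/0.23 = 0.174 (50% vs 70%) to 0.04/0.15 = 0.267 (70% vs 90%).

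- Age 0.5 SD alone: √(1 + 0.250 × 0.25) = 1.031.
- Age 0.8 SD alone: √(1 + 0.250 × 0.64) = 1.077.
- Age 0.5 SD with gender: D² = 0.424 to 0.517, giving 1.052 to 1.063.
- Age 0.8 SD with gender: D² = 0.814 to 0.907, giving 1.097 to 1.108.

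The between-person df fall from 57 to 55 (critical t 2.002 to 2.004). With one summary value per participant, the difference detectable with 80% power is 0.74 SD unadjusted. With both imbalances it becomes 0.78–0.79 SD (age 0.5 SD) or 0.81–0.82 SD (age 0.8 SD), before any gain from explained variance.

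**3. Illustration of the mechanism only.** Suppose there is no group difference net of age and gender. The unadjusted contrast is then shifted by (age imbalance × age–affect correlation) + (difference in proportion of women × gender effect in SD). With 0.5 × 0.2 = 0.10 SD, the unadjusted test rejects 6.6% of the time. With 0.10 + 0.2 × 0.3 = 0.16 SD, it rejects 9.3%. Every input here is assumed.

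**The case against.** The strongest reply is that the stated aim is to compare two groups chosen to be distinct, and for that aim the unadjusted difference is the right quantity. The sentence about why people choose activity is background, not a defined estimand. The one causal phrase in the hypotheses links memory to anticipated affect, not exerciser status to affect, and the SAP addresses that link with a correlation. All of this stands, and it is why the point is modest. It does not settle the matter, because neither document limits the contrast to description and the stated purpose invites a wider reading.

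A second reply is that age, BMI and gender are examined. That is true, and a large joint imbalance would usually show, so readers could weigh it. But comparing is not adjusting, and a non-significant test at this sample size is weak reassurance.

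Two stronger readings are tempting. A reader might infer that the contrast is biased, or that its tests run at 7% or 9% rather than 5%. The documents give neither an imbalance nor any relation of age or gender to affect, so those rates are not properties of this plan. They count as errors only if the age- and gender-adjusted difference is the target. A reader might also infer that adjustment would make the contrast causal. It would not: groups formed by self-reported behaviour can differ in many other ways.

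**Conclusion.** The point holds as a low-cost improvement to consider. As written, the SAP gives a valid description of two groups and no estimate that separates exerciser status from age or gender. The preliminary tests neither exclude an imbalance nor lead to any action. No bias is shown, and its size and direction cannot be derived. The power figures rest on the derived 29 versus 30, two-sided testing at .05 and the assumed imbalances. The randomised comparison among non-exercisers is not affected.

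**What to change.** Keep the unadjusted results. Beside them, report the following with age and gender as fixed covariates, whatever the preliminary tests show:

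- the mixed models for during-exercise, post-exercise and recalled affect;
- a linear model for anticipated affect;
- any group comparison of memory bias.

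Treat BMI as a further sensitivity analysis, because exercise status may itself affect BMI. State that the contrast is associational, even after adjustment. The SAP is written in the past tense, so if the analyses are complete, label the adjusted models as post hoc.

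The cost is two between-person degrees of freedom, a standard error roughly 3% to 11% wider under the imbalances assumed for the precision calculation (less if age and gender explain outcome variance), and a second set of results. No new data are needed, since the SAP already uses age and gender.

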In the week following Exercise Session 1, all participants were asked to maintain their typical daily routines of either exercising or not exercising and respond to an online questionnaire assessing their recall of their own affective responses to the exercise session. These questionnaires were completed 1, 3, and 7 days following the exercise session, and participants responded to the questionnaire by clicking on a link provided via text message. In order to avoid direct recall of responses provided on the Feeling Scale, a VAS was used. On days 1, 3, and 7, participants were asked to reflect upon their Exercise Session 1 by responding to following question; "How do you remember feeling overall?" and this was considered an indicator of *global* affective recall. Following this response on day 7 only, participants were asked to further delineate how they remembered feeling during exercise, and post-exercise. Memory bias was assessed by converting VAS recall values to corresponding FS values and then taking the discrepancy between recalled and actual FS values during and post-exercise (e.g., recalled during exercise affect [assessed 7 days post-exercise] minus actual during

exercise affect [average of Feeling Scale scores every 5 minutes during exercise]. A negative number indicates that participants remembered feeling less positive during exercise than they actually felt. Memory bias for post-exercise affect was computed in a similar manner.

Exercise Session 2

In order to collect data on anticipated affect after participants had experienced one laboratory exercise session, all participants were asked to return to the laboratory for a second exercise session at least 1 week following Exercise Session 1. Exercisers were compensated \$50 for participation in the study, while non-exercisers were randomized, and received a brief PA intervention (described below).

Randomized Controlled Trial for Non-Exercisers

Immediately following Exercise Session 2, all non-exercisers were randomized to a brief, affect-based PA intervention (INT; n=15) or an educational PA intervention, which served as the control condition (CON; n=15).

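### The available SAP text lists no exerciser versus non-exerciser comparison of the day-7 memory-bias score that the protocol defines, and its recall model names no term for experienced affect

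*SAP*

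**What the plan says.** The protocol's Background and objectives asks why people who feel good after exercise do not exercise more, and suggests the answer may lie in "memory of how exercise makes them feel". Among the measures on which the two groups are compared it lists "memory of during and post-exercise affect, and anticipated affect towards a future exercise session". It hypothesizes that "non-exercisers will have a more negative memory of how exercise made them feel".

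The protocol section Affective Recall and Memory Bias collects a global recall item on days 1, 3 and 7. Recall of the during and post phases comes once: "Following this response on day 7 only, participants were asked to further delineate how they remembered feeling during exercise, and post-exercise". It then defines the score: "Memory bias was assessed by converting VAS recall values to corresponding FS values and then taking the discrepancy between recalled and actual FS values", for both phases. Its direction is stated too: "A negative number indicates that participants remembered feeling less positive during exercise than they actually felt".

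The SAP's Statistical analysis section gives a mixed model for recall: "A similar analytic strategy was used to examine group differences in recalled affect (1, 3, and 7 days post-exercise". The stated goal is to learn "the degree to which global recalled affect is associated with (i.e., biased toward) affective responses during or after PA", and whether this differs by group. The bias score appears once, in a correlation with anticipated affect.

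**The concern.** A comparison named in the objectives has a collected measure and a defined score, but the available SAP text gives it no test. The group test that is listed, on recall, answers a different question. If non-exercisers feel worse on the treadmill and remember it accurately, their recall will be lower with no bias at all. The planned models of actual affect may then also show a difference. With both results significant, nothing written says whether memory adds anything beyond experience. Since memory is the study's proposed explanation, a reader could take a lower recall score as support for it when the data do not separate the two.

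**Working it through.** **Matching measures to analyses.** Each recall measure in the protocol, set against the exerciser versus non-exerciser analyses in the available SAP text:

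- Global recall, days 1, 3 and 7: mixed model, with no experienced-affect term named.
- During and post recall, day 7: no group comparison named.
- Memory bias, during and post, day 7: no group comparison; used only in the correlation with anticipated affect.

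The SAP's unadjusted t-tests cover anticipated, pre-exercise and post-exercise affect, not recall. Its ANOVA on recall of session 2 compares the randomized arms within non-exercisers. That the mixed model uses the global item is an inference: the SAP does not name the item, but only the global one exists on all three days, and the next sentence refers to global recall.

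**Size of the ambiguity.** The documents give no effect sizes, SDs or correlations, so there is no plan figure to reproduce.

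*From the documents:* 59 participants; 15 + 15 = 30 non-exercisers; hence 59 − 30 = 29 exercisers, if everyone falls in one of the two groups; significance level .05.

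*Assumed:* two-sided tests; complete data; one recall score per person; recall = actual affect + independent noise (slope 1, no bias in either group); experience difference d = 0.5 SD (range 0.3 to 0.8); recall-experience correlation ρ = 0.7 (range 0.5 to 0.8).

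1. Standard error factor: √(1/29 + 1/30) = 0.260; df = 57.
2. Actual affect: noncentrality 0.5/0.260 = 1.92, power 47% (21% at d = 0.3, 86% at d = 0.8).
3. Recall: the noise variance 1/ρ² − 1 makes the recall SD 1/ρ, so the standardised difference is d × ρ = 0.5 × 0.7 = 0.35. The rejection rate is 26% (9% at 0.3 × 0.5 = 0.15; 68% at 0.8 × 0.8 = 0.64).
4. Joint results, by simulation with 20,000 trials per setting, at d = 0.5 and ρ = 0.7: recall significant 25.7%, recall significant but actual affect not 4.3%, so both significant 25.7 − 4.3 = 21.4%. Over the range, recall alone is significant in 1% to 5%. If the Feeling Scale average has reliability 0.8, the 4% becomes 7% (range 3% to 9%).
5. Under the same model the bias score rejects in about 5%. So does recall adjusted for actual affect, rising to between 5% and 10% with reliability 0.8.

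**Why the bias score should not stand alone.** Suppose recall tracks experience with slope ρ and equal SDs. The bias score then differs between groups by (1 − ρ)d with SD √(2(1 − ρ)), which is d√((1 − ρ)/2) in standardised form. At d = 0.5 and ρ = 0.7 this is 0.5 × √0.15 = 0.194, and the rejection rate is 11%. It is 6% at d = 0.3, ρ = 0.8 and 33% at d = 0.8, ρ = 0.5. If non-exercisers feel worse, this difference runs opposite to the hypothesis.

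**Power of the added test.** Detectable difference at 80% power: (1.960 + 0.842) × 0.260 = 0.73 SD by the normal approximation, 0.74 SD by the t-test.

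**The case against.** - *The hypothesis is already tested.* If more negative memory means only lower recall, the mixed model tests it, and the 26% above is power, not error. That stands for the hypothesis. It does not supply the comparison of during and post memory listed in the objectives.
- *The goal sentence covers bias.* It names experienced affect and a group contrast, so a reader who infers that the plan ignores memory bias goes too far; the score is also used in the correlation. But the sentence concerns association. Two groups can have equal slopes and different mean bias, and no predictor or interaction is written.
- *Day-7 during and post recall might be inside the listed model.* The SAP does not rule this out. These items are at most not named, and global-only is the likelier reading.
- *The affect models would reveal an experience difference.* Often they would, which is why recall alone is significant in only about 4%. The main problem is the larger share in which both are significant.
- *Raw recall always has less power than the bias score.* A reader might infer this, but the documents give no correlation to support it. Take a bias difference that the bias score detects with 80% power, with equal experience. At slope 1 and ρ = 0.7, one recall score per person has 52% power; pooling three days raises this to 59% if half the recall noise is independent across days, and 69% if all of it is. With equal SDs and slope ρ, the two tests tie at ρ = 0.5, and raw recall wins below that (87% at 0.4).
- *Part of the SAP was not available for review.* So the finding is limited to the text that was.

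**Conclusion.** The point holds in limited form. A group comparison named in the protocol, with a score defined for it, has no listed test in the available SAP text, and the recall model as written cannot separate memory from experience. The listed analyses remain valid for what they test. Under the stated assumptions, recall is significant without any memory bias in about 26% of trials (9% to 68% over the range), mostly alongside a significant affect difference. These rates describe a single recall score per person, not the three-day mixed model, and treat global recall as measuring the same thing as the affect score. The conclusion about the missing comparison rests on the text and does not depend on them. This should be fixed, but it is not a fatal flaw.

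**What to change.** 1. Add the exerciser versus non-exerciser comparison of day-7 memory bias, during and post. Report it side by side with day-7 recall adjusted for the matching actual Feeling Scale score, because either one alone can mislead: the difference score when the slope is below 1, the adjusted score when the Feeling Scale is measured with error. Name one outcome (for example, during-exercise) as the main one, and state the conversion from the visual analogue scale to the Feeling Scale. The SAP is written in the past tense, so label these tests as added or post hoc if analysis has begun.
2. Claim a group difference in memory bias only from these analyses. Describe the unadjusted result as a difference in recalled affect.

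A written model for the association goal (global recall on during and post affect, with group interactions) is optional and would be exploratory.

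The cost is a few more analyses of data already collected. Two independent tests at .05 would carry 1 − 0.95² = 9.75% family-wise error, hence the single main outcome. Power is 80% only for a bias difference of about 0.74 SD, and the score depends on the scale conversion.

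### The SAP treats association of global recall with during- or post-exercise affect as bias toward that phase, but association cannot show which phase recall leans on

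*SAP*

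**What the plan says.** The SAP, Statistical analysis, describes mixed models for momentary affect and then turns to recall: "A similar analytic strategy was used to examine group differences in recalled affect (1, 3, and 7 days post-exercise"). The next sentence gives the purpose: "The goal was to determine the degree to which global recalled affect is associated with (i.e., biased toward) affective responses during or after PA", and adds a group comparison, "whether this differs between exercisers and non-exercisers". No during- or post-exercise predictor, coefficient, contrast or reference value for recall without a lean is named for this purpose. The general significance statement is "with significance level set at .05 a priori".

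The Protocol, Affective Recall and Memory Bias, measures global recall with one overall VAS item on days 1, 3 and 7; "this was considered an indicator of *global* affective recall". The same section defines memory bias separately, as recalled minus actual Feeling Scale (FS) score for each phase, using phase-specific items asked on day 7 only. The SAP relates recall bias to anticipated affect by correlation, which is a different question.

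**The concern.** Two questions are being treated as one. An association analysis asks whether global recall is related to affect in a given phase. A question about bias toward a phase asks how much weight that phase carries relative to the other. A person whose overall memory gives both phases equal weight will show association with both, and under the SAP's definition would count as biased toward both.

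The Protocol's memory-bias score does not fill the gap. It measures a shift in level within each phase and says nothing about which phase the overall item follows.

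The group comparison has a related weakness. If association is measured by a correlation, it depends on the spread of affect in each group, so two groups with identical recall weights can have different correlations. The risk is a report that global recall is biased toward one or both phases, or that exercisers and non-exercisers differ in this, when the data show only association.

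**Working it through.** The documents give no effect size, SD, correlation or power figure for this goal, so there is no stated figure to reproduce.

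**Inputs from the documents.** Total N is 59 (Protocol, Participants: "A total of 59 individuals with overweight/obesity"). Non-exercisers are 15 + 15 = 30 (Protocol, Randomized Controlled Trial for Non-Exercisers), which leaves 59 − 30 = 29 exercisers. Alpha is 0.05, taken as two-sided. The SAP analyses five during-exercise and two post-exercise ratings.

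**Assumptions.** Recall is G = w·D + (1 − w)·P + noise, with D and P a person's during and post affect. Both have SD 1.5 FS units, their correlation is 0.5, noise SD is 1, and there is one recall value per person. Then Var(D) = Var(P) = 2.25 and Cov(D, P) = 0.5 × 2.25 = 1.125.

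**Step 1: what association shows.**
- Equal weights (w = 0.5): Cov(G, D) = 0.5 × 2.25 + 0.5 × 1.125 = 1.6875. Var(G) = 0.25 × (2.25 + 2.25 + 2 × 1.125) + 1 = 2.6875. So r = 1.6875 / (1.5 × √2.6875) = 0.69 for both phases. Both are significant in about 100% of simulated trials.
- Lean of 0.8/0.2: Var(G) = 0.64 × 2.25 + 0.04 × 2.25 + 2 × 0.16 × 1.125 + 1 = 2.89. So r = 2.025 / (1.5 × 1.7) = 0.79 for during and 1.35 / (1.5 × 1.7) = 0.53 for post. Both are significant in at least 99% of trials, much as under equal weights.
- During only (w = 1): r with post = 1.125 / (1.5 × √3.25) = 0.42, significant in about 92% of trials although post affect plays no part.
- Equal weights with noise SD 2 and correlation 0.3: each association is still significant in about 91-92%.

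**Step 2: sensitivity to the assumptions.** With unit SDs, during-post correlation 0.3 to 0.8 and noise SD 0.5 to 1.0 at N=59, simple associations under equal weights are significant in 98.6-100%. Tests of each coefficient against zero in a joint model are significant in about 60-100%. With during-only recall, the simple post association is significant in 37-100%.

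**Step 3: group comparison by correlation.** With identical equal weights, correlation 0.5 and noise SD 1, a group with affect SD s has r = 0.75s / √(0.75s² + 1). For s = 1 this is 0.75/√1.75 = 0.57; for s = 2 it is 1.5/√4 = 0.75. A Fisher z comparison of the groups rejects in about 20-26% of trials, although the weights do not differ.

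**Step 4: what a joint model gives.** Regress G on D and P together and take b_D − b_P. Under equal weights the test of zero difference rejects at about 5%; for a 0.8/0.2 lean it has about 90% power. Zero difference is not the same as accurate memory, however:
- An accurate average of the seven analysed ratings weighs during 5/7, a slope difference of 5/7 − 2/7 = 3/7 = 0.43. The test rejects in about 64%.
- An accurate average by time (30 minutes of exercise, 15 minutes after) weighs during 30/45 = 2/3, a slope difference of 1/3. The test rejects in about 45%.

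**Step 5: precision.** SD(D − P) = √(2 × 2.25 × 0.5) = 1.5, and with equal SDs the standard error of b_D − b_P is about 2 × 1/(1.5√n). At n = 59 this is 0.17. For the group difference it is √(0.243² + 0.248²) = 0.35, so the 95% half-width is about 1.96 × 0.35 = 0.68. Weights of 0.8/0.2 against 0.5/0.5 differ by only 0.6 − 0 = 0.6; power is about 35%.

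**Step 6: rating error.** With error SD 0.8 per rating, the error SD is 0.8/√5 = 0.36 for the during mean and 0.8/√2 = 0.57 for the post mean, which favours during. Under equal weights the contrast rejects at about 6% here. It rejects at 12% when post affect has half the spread of during affect in one group. In a harsher setting (unit-SD affect, correlation 0.6, noise SD 0.5, error SD 0.3 for during and 0.6 for post) it rejects at about 27%.

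**The case against.** The strongest reply is that the SAP sentence states a goal about degree and writes no test: no null of zero, no Pearson correlation and no Fisher z for this purpose. It can be read as intending to compare strengths of association. This stands in part. A reader might infer that the plan contains a test that would declare bias in nearly every trial; the documents do not support that, because the rejection rates above belong to procedures supplied for illustration. The comparative reading does not rescue the sentence, since no comparison is specified. Comparing raw correlations would also mislead when spreads differ: with equal weights, correlation 0.6 and noise SD 0.5, a during SD twice the post SD gives r = 0.90 against 0.76.

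A second reply is that equal phase weight is only one possible reference, and that a test of b_D = b_P would itself label an accurate averager as leaning toward during. This stands fully, and is why the slope difference should be an estimate shown against several references.

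A third is that the hypotheses in the Protocol's Background and objectives concern more negative memory, anticipated affect and the intervention effect, and none concerns phase weighting. This also stands. The intervention text does prompt participants to consider which phase they focus on, but as one example question. A reader might infer that this is the mechanism the trial must identify; the documents do not say so.

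**Conclusion.** The point holds as a fault of definition in a secondary goal. Association of global recall with a phase is not bias toward that phase, and neither document supplies a quantity that would show a lean. Under the assumed values at n=59, both associations are significant in about 99-100% of trials whether recall is balanced or leans 0.8/0.2, and the post association in about 92% when post affect is not used at all. The sizes rest on assumed SDs, correlations and noise. The logical gap does not, provided the two phases are correlated or both contribute to recall.

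Two stronger readings should be avoided. The SAP does not contain a written test shown to fail, and a non-zero slope difference would not show that memory is inaccurate. The Protocol's separate memory-bias score is not affected.

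**What to change.** 1. In the SAP sentence, delete the parenthesis that equates association with bias, and report any simple correlations as association only.
2. Fit global recall of Exercise Session 1 (days 1, 3 and 7) in the mixed model with a subject intercept, jointly on each person's mean during-exercise and mean post-exercise FS score, group, and the group interactions. Put recall on the FS scale with the conversion the Protocol already uses for memory bias.
3. Report both unstandardised slopes, their difference, and the group difference in that difference, each with a 95% confidence interval.
4. Describe the slope difference as relative weighting of the phases. Show the references alongside: 0 for equal weight, 3/7 for an average of the analysed ratings and 1/3 for an average by time. These values presuppose weights that sum to 1.
5. Add a sensitivity analysis for unequal rating error in the during and post means.

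The cost is a few lines of SAP text, an ESTIMATE statement in SAS and one sensitivity analysis, with no new data. Two limitations should be stated: the group comparison will be imprecise with about 30 per group, and unequal rating error can distort the slope difference.
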